8.1.2 Treatment Period

Treatment begins on cycle 1 day 1 when the first IV infusion of investigational product is administered to a subject. The study procedures to be completed during the treatment period are designated in the Schedule of Activities (Section 1.3).

The results of the cycle 1 day 1 laboratory tests must be available before starting treatment with tarlatamab. Laboratory assessments that were done within 24 hours prior to infusion do not need to be repeated, except for cycle 1 day 1 dosing where laboratory assessments should be collected within 4 hours before cycle 1 day 1 dosing of tarlatamab. Clinical evaluation should be completed within 6 hours prior to the first dose of tarlatamab.

All assessments and procedures should be collected at the exact nominal time point as noted in the Schedule of Activities. If unable to perform a procedure at the specified nominal time point, collect it as close as possible to the nominal time point and record the actual collection time.

The EOT visit will occur at the end of the last treatment cycle. For subjects who prematurely discontinue IP treatment, the EOT visit should occur as soon as possible after the last dose of investigational product was administered.

Hospitalization Guidance

All subjects will be hospitalized for intensive monitoring for 48 hours post tarlatamab infusion during all cycle 1 doses. Hospitalization is not required for cycle 2 unless a subject experiences grade 2 or higher CRS or neurological events in cycle 1 (minimum of 24 hours hospitalization required post tarlatamab infusion on C2D1 if grade 2 or higher CRS or neurological events are noted in cycle 1). The subjects may be

discharged after this period if there are no signs and symptoms of cytokine release syndrome or other acute toxicities.

Study sites must have immediate access to a medical intensive care unit staffed by critical care providers.

If subjects are not hospitalized during cycle 2, subjects will be observed for 8 hours post tarlatamab infusion.

8.1.3 Safety Follow-up

Upon permanent discontinuation from the study treatment for any reason to further assess the risk of delayed adverse events, an SFU visit will be performed approximately **60 (+5)** days after the end of the last dose of tarlatamab.

The study procedures to be completed during the SFU period are designated in the Schedule of Activities ([Table 1-2](#)).

The following procedures will be completed for patients who have not started subsequent anti-cancer therapy. Additional tests can be conducted at the discretion of the investigator.

- Clinical evaluation
 - Physical examination as per standard of care (including medical/surgical history). Physical examination findings should be recorded on the appropriate eCRF.
 - ECOG performance status
 - Weight
- Vital signs (ie, blood pressure, heart rate, respiratory rate, and temperature)
- Pulse oximetry
- Serious adverse event reporting
- Adverse event reporting
- Documentation of concomitant and rescue medications

This information may be collected by clinic visit, telephone or chart review.

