All subjects will be hospitalized for intensive monitoring for 48 hours post tarlatamab infusion during all cycle 1 doses. Hospitalization is not required for cycle 2 unless a subject experiences grade 2 or higher CRS or neurological events in cycle 1 (minimum of 24 hours hospitalization required post tarlatamab infusion on cycle 2 day 1 if grade 2 or higher CRS or neurological events are noted in cycle 1). The subjects may be discharged after this period if there are no signs and symptoms of CRS or other acute

toxicities. If subjects are not hospitalized during cycle 2, subjects will be observed for 8 hours post tarlatamab infusion.

Routine radiological imaging (computed tomography [CT]/magnetic resonance imaging [MRI]) and tumor burden assessments will be performed as outlined in the Schedule of activities. Assessment of disease response will be determined based on RECIST 1.1 per PCWG3 guidelines (Sections 11.8 and 11.9). To further assess the risk of delayed adverse events, the subject must return for safety follow-up (SFU) visit approximately 60 (+5) days after the last dose of tarlatamab.

Long-term follow-up will be conducted every 3 months up to 3 years from the first dose of tarlatamab for all subjects who have not withdrawn consent by clinic visit, telephone or chart review to assess for survival and/or the commencement of subsequent cancer therapy.

For a full list of study procedures, including the timing of each procedure, please refer to Section 8.2 and the Schedule of Activities in Section 1.3.

Statistical Considerations

All subjects who are enrolled and receive at least 1 dose of tarlatamab will be included in the analysis, unless otherwise specified.

The primary analysis will occur when target enrollment is complete and each subject either completes at least 6 months on study or withdraws from the study. The final analysis will be performed after the last subject has had an opportunity to complete the corresponding end of treatment visit/procedures.

Descriptive statistics will be provided for selected demographics, safety, pharmacokinetic, efficacy data by dose, dose schedule, and time as appropriate.

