- i Safety endocrine panels: Cortisol, TSH, FT4, FSH, LH, testosterone will be evaluated at screening, day 1 of every cycle, EOT, and SFU. ACTH, prolactin, and IGF-1 will be evaluated only at screening and EOT.
- j Cytokines (serum) on day 1 hour 2 will be collected for cycle 1 only.

- p Pharmacogenetic (optional) sample obtained from cell pellet from a biomarker plasma sample at pre-dose (day 1) during cycle 1 only.
- q For visits when subjects are dosed, PK samples should be collected within ± 30 min of the scheduled time points; pre-dose and EOI PK samples should be collected within 30-minutes pre-dose and within 30-minutes post EOI, respectively. For all other non-dosing visits, please follow the window given for procedures stated in Footnote b.
Note: It is important to document the exact time of IP administration and PK collection in the eCRF.
- r Dexamethasone 8 mg IV (or equivalent dose of other corticosteroids) will be administered within 1 hour prior to all doses (including all step dose[s]) of tarlatamab for cycle 1 only.
- s Tarlatamab short-term IV infusion over 60 minutes and a flush. See IPIM for dose administration details. Prophylaxis with IV hydration 1 L normal saline over 4 to 5 hours immediately following all dose(s) in cycle 1 is required.
- t All subjects will be hospitalized for intensive monitoring for 48 hours post tarlatamab infusion during all cycle 1 doses. Hospitalization is not required for cycle 2 unless a subject experiences grade 2 or higher CRS or neurological events in cycle 1 (minimum of 24 hours hospitalization required post tarlatamab infusion on C2D1 if grade 2 or higher CRS or neurological events are noted in cycle 1). The subjects may be discharged after this period if there are no signs and symptoms of cytokine release syndrome or other acute toxicities. If subjects are not hospitalized during cycle 2, subjects will be observed for 8 hours post tarlatamab infusion.
- u Q Cyc: Collected at specified time point beginning with cycle 3 and at each subsequent cycle unless otherwise specified.
- v Q2 Cyc: Collected every 2 cycles starting from cycle 3: C3D1, C5D1, C7D1, C9D1, C11D1
- w Q3 Cyc: Collected every 3 cycles starting from cycle 4: C4D1, C7D1, C10D1
- x SFU visit should be completed **60** (+5) days from the last dose of tarlatamab. For details regarding the tests and procedures to be completed for SFU please refer to Section [8.1.3](#).

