8.2.4.1 Time Period and Frequency for Collecting and Reporting Safety Event Information

8.2.4.1.1 Adverse Events

The adverse event grading scale to be used for this study will be the CTCAE and is described in Section 11.4.

The investigator is responsible for ensuring that all adverse events observed by the investigator or reported by the subject that occur after first dose of investigational product through the **safety follow-up visit or 60 days after the last day of the dosing interval of investigational product(s) or noninvestigational product(s)/auxiliary medicinal product(s), whichever is later**, are reported using the Events CRF.

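### Protocol 8.1.3 makes AE, SAE and concomitant-medication collection at safety follow-up conditional on no new anti-cancer therapy, against 8.2.4.1 and 6.7.2, so primary-endpoint events may be missed

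*Protocol*

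**What the plan says.** Protocol 8.1.3 first provides for an SFU visit after permanent discontinuation for any reason, about 60 (+5) days after the last dose, and points to Table 1-2 for the procedures. It then gives its own list under the condition "The following procedures will be completed for patients who have not started subsequent anti-cancer therapy". The list covers physical examination, ECOG status, weight, vital signs, pulse oximetry, SAE reporting, AE reporting and medication. It closes with "This information may be collected by clinic visit, telephone or chart review".

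Protocol 8.2.4.1.1 makes the investigator responsible for "all adverse events observed by the investigator or reported by the subject that occur after first dose of investigational product through the" SFU visit, or 60 days past the last dosing interval if that is later. Section 8.2.4.1.2 sets the same end point for SAEs, starting from consent. Section 6.7.2 collects concomitant therapies to the end of the SFU period. None of the three mentions new anti-cancer therapy.

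In the Schedule of Activities, footnote x says "For details regarding the tests and procedures to be completed for SFU please refer to Section" 8.1.3. Footnote i says "Cortisol, TSH, FT4, FSH, LH, testosterone will be evaluated at screening, day 1 of every cycle, EOT, and SFU". The synopsis says "the subject must return for safety follow-up (SFU) visit approximately 60 (+5) days after the last dose of tarlatamab".

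The primary endpoint in Protocol Section 3 includes treatment-emergent and treatment-related AEs. SAP Section 5.2 counts an AE as treatment-emergent up to 47 days after the last dose, with no cut at new therapy.

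**The concern.** One section conditions what three others require of everyone, and the schedule directs sites to the conditional section. A coordinator preparing an SFU contact for a subject already on another treatment could reasonably conclude that no AE, SAE or medication enquiry is due.

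The data at risk are the primary safety data, in the period that 8.1.3 itself says is there to detect delayed events. Because the SAP does not close the treatment-emergent window at new therapy, a subject whose reporting stopped early would be analysed as though observed for the whole window. Collection could also differ among the approximately 25 sites, according to which section each follows. Events that were never collected cannot be recovered at analysis.

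**Working it through.** **Step 1. The passages side by side.**

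| Place | Items | Who | Until |
|---|---|---|---|
| Protocol 8.1.3 | AE, SAE, medication, examinations | Subjects not on new therapy; silent on the rest | SFU visit |
| Protocol 8.2.4.1.1 | AEs | All | SFU visit, or dosing interval + 60 days if later |
| Protocol 8.2.4.1.2 | SAEs | All | Same |
| Protocol 6.7.2 | Concomitant therapies | All | End of SFU period |
| SAP 5.2 | Treatment-emergent AEs | All | 47 days after last dose |

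**Step 2. Do the cross-references settle it?** Section 8.1.3 points to Table 1-2, and footnote x of that table points back to 8.1.3. The loop ends at the conditional list. The AE, SAE and medication rows of Table 1-2 are drawn as bars whose extent is not readable in the extracted text, so whether they run through SFU could not be checked.

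**Step 3. Days exposed in the analysed endpoint.** Inputs: window W = 47 days (SAP 5.2); start of new therapy s = 14, 28 or 42 days after the last dose (assumption; the documents give no figure). Exposed days = W − s.
- s = 14: 47 − 14 = 33 days (33/47 = 70%)
- s = 28: 47 − 28 = 19 days (19/47 = 40%)
- s = 42: 47 − 42 = 5 days (5/47 = 11%)

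**Step 4. Days exposed in the reporting duty.** With dosing every 2 weeks, the 8.2.4.1 window is 14 + 60 = 74 days after the last dose. For the same start days, 74 − s = 60, 46 or 32 days. Days 48 to 74 lie outside the current treatment-emergent definition, so these figures describe the reporting duty, not loss to the analysed endpoint.

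**Step 5. Effect on detection, as illustration only.** Protocol 9.2 states that 40 subjects give an 87% chance of seeing at least one AE of 5% incidence: 1 − 0.95^40 = 0.871, which reproduces it. Suppose an event occurred only during follow-up, and a share of the 40 subjects was not covered at all. The shares below are assumptions.
- 25% uncovered (n = 30): 1 − 0.95^30 = 0.785
- 50% uncovered (n = 20): 1 − 0.95^20 = 0.642
- 75% uncovered (n = 10): 1 − 0.95^10 = 0.401

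This is a worst case, since it gives no credit to events reported under 8.2.4.1.

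**Step 6. Two secondary mismatches in 8.1.3.** The list has no laboratory test, while footnote i requires a hormone panel at SFU. The closing sentence allows remote collection of the listed items, although weight, vital signs and pulse oximetry cannot be newly measured by telephone and the synopsis requires the subject to come back.

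**The case against.** The strongest reply is that 8.1.3 exempts nobody. It lists visit procedures for one group and says nothing about the other, while 8.2.4.1 places an unconditional duty on the investigator. Other sections support that duty: 7.1 asks that subjects stay on study after stopping treatment, 8.2.4.3 follows events to resolution or stabilization, and 8.2.4.1.3 requires related SAEs to be reported during long-term follow-up. This stands as far as it goes. It shows that events are not certain to be lost; it does not show that a site sent to 8.1.3 by footnote x will apply the wider rule.

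A reader might infer that the telephone sentence lets a call replace the endocrine panel, so that late pituitary dysfunction would go undetected. The documents do not support this. The sentence covers only the listed items, the panel is not among them, and both footnote i and the pointer to Table 1-2 keep it required. Symptoms can also be asked about by telephone.

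A reader might also take the 74-day figures (60/74 = 81%, 46/74 = 62%, 32/74 = 43%) as loss to the primary endpoint. They are not, because the SAP stops counting at 47 days.

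**Conclusion.** The contradiction is real and bears on the primary endpoint. A site that follows 8.1.3 may stop collecting AEs, SAEs and medications at the start of new therapy, while the SAP analyses the subject to day 47 regardless. For assumed starts on day 14, 28 or 42, 33, 19 or 5 of the 47 days are exposed.

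These are days at risk of non-collection, not a measured loss: they assume that nothing is captured after new therapy starts, despite 8.2.4.1. The share of subjects who start new therapy before SFU is not in the documents. Any head count, such as 12 to 24 of the 40 expansion subjects (30% to 60% of 40), would rest wholly on an assumption and should not be read as a finding.

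The 47 days come from a SAP written for protocol Amendment 6, when SFU fell at 42 (+5) days; the protocol now has 60 (+5). If the SAP window is lengthened to match, the exposed days grow. The point does not depend on that. The panel and telephone mismatches are secondary matters of consistency.

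**What to change.** In Protocol 8.1.3, take AE reporting, SAE reporting and concomitant medication out of the conditional list. State that they apply to all subjects for the full 8.2.4.1 window whether or not new anti-cancer therapy has started, and that the start date of such therapy is recorded. The condition can stay on the on-site tests.

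In the same edit, reconcile the 8.1.3 list with the SFU column of Table 1-2 and footnote i. Also reconcile the remote-collection sentence with the synopsis by limiting it to items that can be obtained remotely.

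The cost is wording in one section and a few more AE queries for subjects on new therapy. Some of the added events will be confounded by that therapy; the recorded start date lets the analysis show which ones.

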8.1.4 Long-term Follow-up

Long-term follow up will be conducted every 3 months up to 3 years from the first dose of tarlatamab for all subjects who have not withdrawn consent by clinic visit, telephone or chart review to assess for survival and/or the commencement of subsequent cancer therapy only.

For subjects who discontinued treatment for any reason other than confirmed progressive disease, every effort should be made to perform radiographic imaging (CT/MRI/bone) of the chest, abdomen, pelvis, bone, and all other known sites of disease every 3 months until documentation of confirmed disease progression per PCWG3 guidelines (Sections 11.8 and 11.9), clinical progression, start of new anticancer therapy, or up to 3 years after the first dose of tarlatamab, whichever occurs first.

8.2 Description of General Study Assessments and Procedures

The sections below provide a description of the individual study procedures for required time points.

8.2.1 General Assessments

8.2.1.1 Informed Consent

All subjects or their legally authorized representative must sign and personally date the **external review body** approved informed consent before any study-specific procedures are performed.

8.2.1.2 Demographics

Demographic data collection including sex, age, race, and ethnicity will be collected in order to study their possible association with subject safety and treatment effectiveness. Additionally, demographic data will be used to study the impact on biomarkers variability and PK of the **investigational product(s)**.

8.2.1.3 Medical History

The investigator or designee will collect a complete medical and surgical history that started prior to enrollment through the time of consent. Medical history will include information on the subject's concurrent medical conditions. Record all findings on the medical history eCRF.

Relevant medical history, including antecedent hematologic or oncologic disease, other diseases/symptoms such as fatigue, bleeding and infection (resolved and ongoing) will be collected. The current toxicity grade will be collected for each condition that has not resolved. Any unresolved medical history will be graded according to Common Toxicology Criteria for Adverse Events (CTCAE) version 4.0 (Section 11.4) unless specified otherwise.

All prior cancer treatment therapies will be collected.

8.2.1.4 Physical Examination

Physical examination will be performed as per standard of care. Physical examination findings should be recorded on the appropriate CRF (eg, medical history, event).

8.2.1.5 Physical Measurements

Height in centimeters should be measured without shoes. Weight in kilograms should be measured without shoes.

8.2.1.6 Performance Status

ECOG performance status (Section 11.10) assessments will occur at time points specified in the Schedule of Activities (Section 1.3).

8.2.1.7 Neurological Examination

A neurological examination will be performed as outlined in the Schedule of Activities (Section 1.3). Subjects will be specifically queried for neurological symptoms observed in the interval since the last extended neurological examination. Abnormalities of the following should be recorded: level of consciousness, orientation, vision, cranial nerves and brain stem functions, pyramidal and extra pyramidal motor system, reflexes, muscle tone and trophic findings, coordination, sensory system, neuropsychological findings (eg, speech, cognition and emotion).

The individual performing the neurological examination will characterize the findings as either normal or abnormal. Abnormal findings found predose will be reported on the medical history page of the eCRF. Abnormal findings found after the subject is dosed will be reported on the Event page of the eCRF.

A more detailed neurological assessment may be performed in subjects at selected sites.

8.2.1.8 Writing Test

Subjects will be asked to provide writing tests in order to detect early cerebellar signs as outlined in the Schedule of Activities (Section 1.3). Subjects will write down the current date, location of the clinic, and the current time in a sentence. The sentence format should be repeated each time throughout the study. Interpretation of writing sample results will be based solely on the investigator's assessment.

8.2.1.9 Mini-Mental Status Examination

The Mini Mental Status Examination (MMSE) Version 2 will be performed as part of the Clinical Evaluation as outlined in the Schedule of Activities (Section 1.3). The MMSE is a 30-point healthcare professional administered questionnaire to assess potential

subjects for cognitive impairment. The assessment covers eight categories, such as orientation to time, orientation to place or language, with a total score that ranges from 0 to 30 (30 indicates the best possible outcome). The overall total score should be recorded on the appropriate eCRFs.

[figure not shown]
8.2.2 Efficacy Assessments

8.2.2.1 Radiologic Imaging Assessment

Radiographic assessments will be obtained as scheduled in Section 1.3 irrespective of cycle duration including dose delays and treatment discontinuation.

For subjects developing COVID19 during screening period following screening imaging, consider repeating CT of chest imaging following resolution.

Standard radiological assessments should take place until clinically significant disease progression or deterioration, withdrawal of consent, or start of new anticancer therapy. Every assessment must include the chest, abdomen, and pelvis, all other known sites of disease and magnetic resonance imaging (MRI) of the brain if a subject has signs or symptoms suggestive of CNS metastases. The MRI/CT can be obtained earlier if clinical deterioration necessitates an earlier scan at the discretion of the managing physician. The same contrast and modality used at screening should be used for all subsequent assessments. ^{99m}Tc-MDP (^{99m}technetium methylene diphosphonate) bone scan is required for each radiologic imaging and tumor assessment.

Tumor burden assessments will be performed per PCWG3 guidelines (Sections 11.8 and 11.9). To confirm soft tissue disease progression, a second MRI/CT scan must be performed at least 4 weeks after the first detection of soft tissue disease progression. Responses (partial response [PR] and complete response [CR]) require confirmation by a repeat consecutive assessment at least 4 weeks after the first detection of response as measured by RECIST 1.1. Planar bone scintigraphy must be performed using

conventional ^{99m}technetium methylene diphosphonate radionuclide (^{99m}Tc-MDP) or other equivalent ^{99m}Tc-labeled radiotracers. Confirmation of bone disease progression by bone scan should be performed per PCWG3 guidelines. Disease progression based on both MRI/CT and bone scans will be used in radiographic progression endpoints (eg, radiographic PFS) evaluation. Soft-tissue progression based on MRI/CT scan will be used in response endpoints (eg, objective response and DOR) evaluation. Treatment beyond confirmed tumor progression may be allowed as per PCWG3 guidelines (Section 11.8; Scher et al, 2016). Refer to the imaging manual for details on imaging assessments.

8.2.3 Safety Assessments

Planned time points for all safety assessments are listed in the Schedule of Activities see (Section 1.3).

8.2.3.1 Vital Signs

The following measurements must be performed: systolic/diastolic blood pressure, heart rate, respiratory rate, and temperature. Subject must be in a supine position in a rested and calm state for at least 5 minutes before blood pressure assessments are conducted. If the subject is unable to be in the supine position, the subject should be in most recumbent position as possible. The position selected for a subject should be the same that is used throughout the study and documented on the vital sign CRF. The temperature location selected for a subject should be the same that is used throughout the study and documented on the vital signs CRF. Record all measurements on the vital signs CRF.

